## JHM IRB - eForm A – Protocol

### 1. Abstract

Medical, psychosocial and financial problems associated with prenatal opioid dependency and Neonatal Abstinence Syndrome (NAS) have reached epidemic proportions in the US. Solutions include optimizing the treatment for opioid dependent pregnant women while mitigating the severity of NAS and other neurobehavioral consequences of prenatal opioid exposure. Currently, only methadone maintenance is offered standardly, with more providers prescribing buprenorphine-only in the US due to milder NAS. Methadone treatment, although advantageous for many women, is a difficult choice due to the frequency and severity of the NAS. Buprenorphine-only has a high diversion/abuse potential, is not always readily available, and can have unpleasant side effects in some women. Buprenorphine-naloxone (B+N) treatment of pregnant women may be an attractive and effective strategy due to the antagonist component, which can result in reduced abuse liability, reduced risk of diversion and increased drug effectiveness by increasing medication adherence, all of which can serve to decrease NAS severity. However, there are currently no published reports that provide a prospective assessment of maternal, fetal and infant functioning with maternal B+N maintenance.

The purpose of this study is to evaluate the effects that maternal B+N maintenance have on the neurobehavioral development of the fetus and infant. To accomplish this, we will study a sample of  $n=80$  (considering a recidivism rate of 50% for  $n=40$  protocol completers) opioid dependent pregnant women that will receive B+N as part of substance abuse treatment at a comprehensive care treatment facility for pregnant and parenting women with substance use disorders, or stable patients receiving B+N from other treatment providers who are willing to a) complete the Addiction Severity Index (ASI) around the time of consent, b) consent to a review of medical records, c) leave weekly research urines for the study team and d) plan for delivery at the JHBMC hospital. A matched sample of  $n=80$  (considering a recidivism rate of 50% for  $n=40$  protocol completers) methadone maintained women will be recruited as a comparison sample. Fetal neurobehavior and maternal physiology will be assessed, via an established maternal-fetal data acquisition system, at 4 points during gestation: 24, 28, 32 and 36 weeks. Infant birth parameters and NAS spectrum display will be evaluated at birth, and infant neurodevelopment will be assessed during the first month of life. We will compare the neurodevelopment of the B+N-exposed fetuses and infants to that of the comparison group of methadone and a historical (2012-2016) group of buprenorphine-only exposed fetuses and infants. Additionally, among a subsample of participants who wish to and are eligible to breastfeed their infants, we will evaluate maternal plasma, breast milk and infant plasma concentrations of buprenorphine, naloxone and their major metabolites.

### 2. Objectives (include all primary and secondary objectives)

*Aim 1:* Determine the acute effects of B+N and methadone exposure on the fetus by comparing fetal neurobehavior at times of peak and trough maternal B+N levels during the second half of gestation (24,28,32 and 36 weeks).

*Hypothesis 1a:* Fetal heart rate and motor activity patterns indicative of fetal well-being will be attenuated when maternal circulating B+N and methadone is at its peak as compared to trough concentration.

*Hypothesis 1b:* Differentials in fetal heart rate and motor activity patterns between peak and trough will increase over the course of gestation as neurobehavioral development becomes more organized.

*Hypothesis 1c:* The differential in fetal heart rate and motor activity patterns at peak and trough will be reduced in fetuses of B+N maintained mothers as compared to a matched cohort of methadone exposed fetuses, and will show either no difference or greater attenuation when compared to buprenorphine-only exposed fetuses.

*Aim 2:* Evaluate the development of the B+N-exposed fetus, and compare this with two other treatment exposures (a matched prospective methadone maintained group and a recent historical buprenorphine-only group).

*Hypothesis 2a.:* Fetal heart rate and motor activity patterns indicative of greater fetal well-being, and their developmental trajectory, will either not differ between B+N and buprenorphine-only groups at 24, 28, 32 and 36 weeks gestation, or they will be indicative of more optimal neurodevelopment. Separate comparisons will be made at both trough and peak levels to allow examination of both acute and chronic effects.

*Hypothesis 2b:* Fetuses of B+N maintained mothers, as compared to a matched cohort of methadone exposed fetuses, will exhibit fetal heart rate and motor activity patterns indicative of greater fetal well-being.

*Aim 3:* Determine the differential effects on the infant's NAS expression in B+N as compared to the other two treatment exposures (matched methadone exposed and historical buprenorphine exposed infants).

*Hypothesis 3a:* B+N-exposed infants will have mild NAS

*Hypothesis #3b:* B+N exposed infants will have less severe NAS symptomatology than methadone exposed infants, consist with current literature.

*Hypothesis #3c:* B+N exposed infants will have similar NAS severity relative to buprenorphine-only exposed infants.

*Hypothesis #3d:* An additional exploratory subaim will seek to identify other maternal physiologic and/or fetal neurobehavioral markers that may predict NAS severity.

*Aim #4:* Will evaluate the longitudinal neurobehavioral developmental profile of B+N exposed infants up to 1 month of age. Infant neurobehavioral development will be compared to a matched cohort of methadone exposed and a historical cohort of buprenorphine only exposed infants.

*Hypothesis#4a:* B+N-exposed infants will evidence mild neurobehavioral alterations in the first month.

*Hypothesis #4b:* B+N-exposed, as compared to methadone-exposed infants will exhibit less severe neurobehavioral alterations.

*Hypothesis #4c:* The neurobehavioral functioning of the B+N and buprenorphine-only exposed infants will be similar.

*Aim #5:* Will evaluate concentrations of B+N in breast milk, maternal and infant plasma among breastfeeding women maintained on B+N.

*Hypothesis #5a-c:* B+N concentrations in a) maternal plasma, b) breast milk c) infant plasma will be low

*Hypothesis #5d:* B+N concentrations in breast milk, maternal plasma and infant plasma will be related to maternal dose of B+N.

### **3. Background**

The PI's main clinical focus for the past 26 years has been the development of a highly successful model of care for the population of infants and children of women with substance use disorders. The PI has directed

the pediatric component of the Center for Addiction and Pregnancy since the program's inception and continues to provide pediatric care to the children of women with substance use disorders who attend comprehensive drug treatment. Research based on this population has been afforded by an initial K-award and two subsequent investigator-initiated awards. All aforementioned awards evaluated maternal maintenance medication effects on fetal and infant development. This research has followed the clinical uses of various medications in pregnancy for the treatment of opioid dependency. The initial K award (2000-2005) and first RO1 (2005-2010) evaluated methadone (i.e. full agonist) effects, the second RO1 (2011-2016) evaluated buprenorphine (i.e. mixed agonist-antagonist) effects. The next logical step in the progression of this research is the evaluation of B+N (i.e. buprenorphine (mixed agonist-antagonist) + full antagonist) use in pregnant opioid dependent women and fetal and infant effects. All studies to date have recruited subjects from the CAP program, and all have used the same computerized maternal physiology and fetal neurobehavioral assessment paradigm. Inclusion and exclusion criteria are essentially the same for all projects.

#### **4. Study Procedures**

##### **a. Study design, including the sequence and timing of study procedures:**

No procedures described here are part of routine patient care.

Participants will be selected from a population of women with OUDs in substance use disorder treatment at the Center for Addiction and Pregnancy (CAP), a comprehensive care treatment facility located in Baltimore and providing treatment for substance use disorders, mental health services, obstetric care and pediatrics (Jansson, 1996), which has been the site for all previously described research activities. Additional participants may include stable pregnant patients who are maintained on B+N in treatment by other providers who are willing to leave weekly research urines for toxicology testing and undergo fetal testing procedures. Total subject enrollment will be 160 (80 methadone and 80 B+N) participants; using a conservative estimate of 50% non-completion, the final sample size will be 80 (40 methadone and 40 B+N) mother/infant dyads.

Women accepting or requesting buprenorphine treatment will be offered study participation at the time of their contact with CAP intake staff after indicating a willingness to talk to study staff regarding research. The methadone comparison sample ( $n=80$ ) will be drawn from the population of CAP methadone maintained women and matched on . severity of OUD (route of administration (IV vs other) Eligibility for study enrollment and B+N maintenance will be determined by the project obstetrician and psychiatrist prior to study enrollment. B+N dose after induction to medication will be determined and regulated by the psychiatrist with adjustments made at the recommendation of patient counselors based on subjective and objective indicators of withdrawal or over-medication symptoms. All medication dosing will take place at an observed medication window. Take-home dosing will be afforded for holidays, inclement weather, or at the discretion of the project psychiatrist with input from the subject's counselor for other reasons on an individualized basis. Participants enrolled from other treatment programs will be informed of the study at their treatment program and asked to contact study personnel if they are interested.

Stable buprenorphine or B+N women wishing to be enrolled in the protocol will not undergo induction, but will be admitted to the study after confirmation from their current prescribed of their medication status and dose. They will receive their current dose, with adjustments to be made at the discretion of their therapist and the overseeing psychiatrist.

**B+N induction protocol:** Subjects will be asked to not use heroin or other opioids for at least 10 hours and be in mild withdrawal at the time of enrollment. B+N filmstrips will be administered sublingually at the discretion of the prescribing physician. Participants will be instructed to hold the filmstrips under their tongue until dissolved without talking. All dosing will be observed. All alterations in dose during the induction period and beyond will be at the discretion of the project psychiatrist(s) and obstetrician.

Maximum dose on day 1 and 2, except as determined by project physicians, is 10 and 16 mg, respectively. The co-investigator obstetrician will be aware of all B+N inductions and will facilitate transfer to the on campus Labor and Delivery suite for management of somatic complaints that are not manageable in the outpatient setting. All women will provide urine for toxicology testing prior to the initial dose each day to assure that no agonist opioids have been taken. Subjects that take illicit or licit opioids during the evenings of the induction period, by history or urine toxicology screening, may be removed from the protocol.

All participants receiving B+N will receive the following instructions regarding dosing: No smoking for 15 minutes prior to dosing. The participant will be asked to take a drink of water to increase stickiness of filmstrip. Hold medication under the tongue until dissolved.

Control and confounding measures: Research on pregnant women with opioid use disorder presents unique and well-known challenges. Polydrug licit and illicit substance use, other psychiatric comorbidities, and correlates of unhealthy lifestyles all may contribute independently to fetal neurobehavioral development and pregnancy outcomes. Highly restrictive criteria for enrollment to exclude factors, particularly those related to polydrug exposure so that effects of B+N can be isolated, results in small and non-representative samples. Less restrictive exclusionary criteria but subsequent controlling for confounders will result in larger samples and more generalizable data, but raises threats to interpretation of final results. The PI's 26 years of clinical experience working with this population has provided extensive expertise regarding the nature and extent of these factors and the complexities inherent in pregnant opioid dependent women's lives. The proposed project period will use a less restrictive enrollment approach, inducting women to B+N maintenance and following subsequent substance use closely; and not dis-enrolling them in the event of relapse. Fetal testing will not proceed if women have positive urine toxicology indicating illicit substance use or licit substance misuse at the time of testing to exclude the occurrence of fetal measures affected by acute effects of substances. An exception will be a positive toxicology for marijuana if the subject has denied recent (within the last 24 hours) use, as chronic marijuana users will have urine toxicology that remains positive for many weeks after cessation of use. The marijuana positive group will be analyzed as a subpopulation.

*Maternal medical and obstetrical history.* Maternal health records will be abstracted for past/current medical history, past/current obstetrical history and current medications.

*Maternal drug abuse history, demographic information and psychosocial history.* Information will be abstracted from maternal health records and from the Addiction Severity Index (ASI; McLellan, 1992) which will be administered to all subjects at the time of enrollment. This standardized clinical interview provides data regarding substance use history (lifetime; past 30 days), and functional impact and use severity in 7 areas. The domains of drug and alcohol use and psychological functioning will be reviewed and abstracted for study purposes. Information abstracted from maternal health records will include current/past obstetrical and medical histories, drug abuse treatment history and current B+N dose. Program intake assessment and medication records for each subject are reviewed at the time of consent as well as at the time of testing.

*Withdrawal symptomatology.* To verify appropriate dosing, women will be asked for a subjective report using two questionnaires at the time of fetal monitoring. On the Adjective Questionnaire (Eissenberg, 1996; Preston, 1988) respondents use a 5-point scale to rate 21 withdrawal symptoms (i.e. watery eyes, muscle cramps) intermixed with 16 agonist adjectives (i.e. nodding, itchy skin). The Clinical Opiate Withdrawal Scale, (COWS; Wesson, 2003) assesses 11 common signs and symptoms of opiate withdrawal, with each item rated on a scale; scores below 12 reflect minimal or mild withdrawal. While we regard this as a necessary control measure, no subject in the previous project period had been determined to be in significant opioid withdrawal at the time of fetal monitoring.

*Ascertainment of illicit substance use/licit substance misuse:* Quicktest urine screening, which will include testing for buprenorphine (10 ng/mL), amphetamines (1000 ng/mL), barbiturates (300 ng/mL), benzodiazepines (300 ng/mL), cocaine (300 ng/mL), methadone (300 ng/mL), methamphetamines (1000 ng/mL), opiates (300 ng/mL), oxycodone (100 ng/mL), and THC (50 ng/mL), for a total of once weekly screening, will occur for CAP participants and those from other treatment programs. These urine toxicology screens will be performed by research staff. Participants will undergo urine toxicology screening at the time of each fetal monitoring session. Urine toxicology screening that is positive, i.e. representative of illicit substance use or licit substance misuse, at the time of fetal testing will result in cancellation of the fetal monitoring procedures for that day, with the exception of marijuana (see above).

*Ascertainment of other substances.* Alcohol is a well-known fetal teratogen, and chronic fetal exposure to alcohol will be excluded in the study populations. Any woman meeting DSM V or ASI criteria for alcohol use disorder will not be enrolled. We will also attempt to identify women using alcohol acutely; recent alcohol use will be verified with participant interview. Positive clinical screens for alcohol use will also be tracked via chart review. Women having evidence of or reporting recent alcohol use more than three times during the period of study enrollment will be removed from the protocol; however alcohol use emerged as a disenrollment criteria in only one participant in the prior study, likely due to our exclusion of alcohol use disordered participants based on ASI screening. In contrast to the low levels of alcohol use in our participants, cigarette smoking is routine, reflecting the larger CAP clientele: 88.5% use nicotine. Self-report data will be collected from each participant regarding the average number of cigarettes smoked per day upon enrollment and at each testing point. Women will be asked to refrain from smoking for 2 hours prior to each maternal-fetal recording. Nicotine withdrawal is unlikely in this time frame, and pregnant women are less likely to report any nicotine withdrawal in the first 24 hours of abstinence than non-pregnant women (Ussher, 2012).

*Maternal psychiatric characteristics.* Approximately 75% of CAP clients report a current history of psychological problems at program intake, and more are diagnosed during treatment. All CAP clientele are referred for psychiatric evaluation after admission and near 40% receive medication, primarily selective serotonin reuptake inhibitors (SSRIs) prescribed for depression, the major Axis I disorder among CAP clients. However, many choose not to take these medications. Psychiatric diagnoses, medications prescribed and medications taking will be recorded for each subject.

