*Infant variables.* Infant testing using the NNNS generates 13 summary scores (habituation, attention, handling, quality of movement, regulation, non-optimal reflexes, asymmetric reflexes, stress/abstinence, arousal, hypertonia, hypotonia, excitability and lethargy) that have been normatively described for both substance exposed and non-exposed infants (Tronick, 2004). Exploratory data analysis techniques will be used to determine distributions for each measure to determine how many of these will be used in the final analysis.

*Breastmilk variables:* Concentrations of B+N and major metabolites in breast milk, maternal and infant plasma

b. Statistical plan including sample size justification and interim data analysis.

*Fetal studies:* Individual analyses will be performed for three cardiac measures (FHR, FHR variability and accelerations) and two motor variables (overall activity, bout duration), and two synthetic measures (event and time series-based FM-FHR coupling, as described in the Procedures section. We will also evaluate effects of BN on maternal physiological function (heart period, respirations, cardiac vagal tone, skin conductance, and blood pressure).

Models for aims 1 and 2 will be longitudinal mixed effects linear regression models with random intercepts (Fitzmaurice, 2011). Additional models with fetal sex interactions will be fit to evaluate whether boys are differentially affected by either exposure, as we have observed in previous evaluating neurobehavior in methadone exposed infants (Jansson, 2010). Additionally, all analyses will be adjusted for maternal age, race, and non-opioid substance use.

For Hypothesis 1A, we will fit a model where the outcome for the  $i$ th individual at the  $j$ th timepoint ( $y_{ij}$ ) =  $\beta_0 + \beta_1 \text{peak} + \beta_2 \text{p}_2 - \text{p}_1 + \epsilon_{ij}$ , and  $\beta_1$  represents the difference, across timepoints, in the outcome between peak and trough measurements. For Hypothesis 1B, we will fit a similar model,  $y_{ij} = \beta_0 + \beta_1 \text{peak} + \beta_2 \text{time} +$

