$\beta_3\text{peak} * \text{time} + \beta_4 \cdot \text{pX4\_p} + \varepsilon_{ij}$ , where  $\beta_3$  represents the rate of change in the difference in outcome between peak and trough over time. For Hypothesis 1C, we will fit a model where  $y_{ij} = \beta_0 + \beta_1\text{peak} + \beta_2\text{BN} + \beta_3\text{peak} * \text{BN} + \beta_4 \cdot \text{pX4\_p} + \varepsilon_{ij}$ , where  $\beta_3$  represents the between-treatment (BN-Methadone) or (BN-Buprenorphine) difference in peak-trough differences. Additionally, we will fit a model with a 3-way interaction between peak, time, and BN to determine if changes over time in peak-trough differences vary between BN and Buprenorphine.

For Hypothesis 2A, we will fit models separately for peak and trough measures where  $y_{ij} = \beta_0 + \beta_1\text{BN} + \beta_2 \cdot \text{pX2\_p} + \varepsilon_{ij}$  where  $\beta_1$  represents the difference in outcome between BN and Bup. We will also fit models where  $(y_{ij}) = \beta_0 + \beta_1\text{BN} + \beta_2\text{time} + \beta_3\text{BN} * \text{time} + \beta_4 \cdot \text{pX4\_p} + \varepsilon_{ij}$ , and  $\beta_3$  represents the difference in outcome trajectory over time between BN and Buprenorphine. For Hypothesis 2B, we will fit a model similar to 2A but only using data from 36 weeks to compare methadone and BN.

*Neonatal study:* For hypothesis 3A, we will use descriptive statistics to characterize NAS in BN-exposed infants, as measured by mean daily NAS scores on days 1-4 of life, highest NAS score, amount of medication (morphine sulfate, mg) required to treat NAS, number of days treated for NAS, and total days hospitalization. For hypothesis 3B, we will fit models of NAS severity (measured by Day 3 Finnegan scores, total medication used to treat NAS, total days of NAS treatment and total days of hospitalization), as a function of BN exposure (compared to methadone exposure), adjusting for maternal age, race, and non-opioid substance use. The models for hypothesis 3C will be analogous, but with buprenorphine exposure as the comparator. For hypothesis 3D, we will examine additional predictors of NAS severity including infant sex (Warren, 2015), daily and cumulative dose of BN, other medications including SSRIs (dosage and categorical), illicit drug use based on number of “dirty” urines and specific substance exposures, cigarette smoking (cigarettes per day and CO levels).

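### Beyond a binary IV-versus-other route match for the methadone comparison, no planned group model controls for opioid-use or psychiatric severity, although the ASI measures both in every enrolled woman

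*Combined protocol and SAP*

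**What the plan says.** **How the groups form.** Section 4a recruits the B+N group by patient choice: "Women accepting or requesting buprenorphine treatment will be offered study participation". It adds a second source: "Additional participants may include stable pregnant patients who are maintained on B+N in treatment by other providers". Methadone women come only from the CAP clinic. Section 5 bars women with more than three consecutive days of methadone dosing or street methadone use from the B+N group only.

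**The match.** The methadone sample is matched on "severity of OUD (route of administration (IV vs other". The words after the matching verb are missing and the bracket is not closed, so other factors may have been lost. Severity itself is defined by route. No matching is described for the historical buprenorphine-only group.

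**What is measured.** Section 4a describes the ASI, "which will be administered to all subjects at the time of enrollment", as follows: "This standardized clinical interview provides data regarding substance use history (lifetime; past 30 days), and functional impact and use severity in 7 areas". The drug and alcohol and the psychological domains are abstracted for the study. The only further use stated is screening for alcohol use disorder.

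**What is adjusted for (Section 7b).**
- Aims 1 and 2: "all analyses will be adjusted for maternal age, race, and non-opioid substance use".
- Hypothesis 3B, with 3C analogous: "adjusting for maternal age, race, and non-opioid substance use".
- Aim 4: age, race, dosing and other substance use.
- The exploratory NAS predictors under 3D include SSRIs, urine results and smoking, but neither ASI scores nor route.

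**The concern.** Two women who both inject, or who both do not, can differ widely in duration of use, recent use and functional impairment. A route match leaves that variation free. The adjustment set covers non-opioid substances, so it does not address opioid-use severity.

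The psychiatric side has no match at all. Section 4a names psychiatric comorbidity among factors that may act independently on fetal neurobehavior and pregnancy outcome. It chooses permissive entry criteria on the understanding that confounders will be controlled later, and it puts current psychological problems at about 75% of clinic clients at intake. No listed group model carries a psychiatric severity term.

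The two recruitment sources and the methadone-exposure exclusion, which applies to one group only, give grounds within the plan to expect that opioid histories could differ between groups. The match is also made on 80 enrolled women per group, while 40 are expected to complete. A match at enrolment need not hold among completers.

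At stake are the between-group level contrasts in 2a, 2b, 3b, 3c, 4b and 4c. Hypotheses 3c and 4c predict similarity and 2a allows no difference. In those, confounding could hide a real difference as easily as create a false one.

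**Working it through.** **Step 1. The plan's own figures.** Inputs from Section 7b: alpha 0.05 (two-sided assumed, since sidedness is not stated), power 0.80, 40 completers per group.

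| Hypothesis | Stated difference / SD | Effect (SD) | t-test power, 40 v 40 |
|---|---|---|---|
| 1 | 4.23 / 6.68 | 0.633 | 79.9% |
| 2 | 4.12 / 6.49 | 0.635 | 80.1% |
| 3 | 0.63 | 0.630 | 79.5% |
| 4 | 0.44 / 0.70 | 0.629 | 79.3% |

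Enrolment: 40 / (1 − 0.5) = 80 per group, 160 in total. The stated figures reproduce. The sample size is not in question; the issue is bias.

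**Step 2. Size of a possible bias.** The documents give neither a severity gap nor a severity-outcome correlation, so both are assumptions.

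Bias (SD) = residual gap (SD) × correlation. The standard error of a difference at 40 per group is √(2/40) = 0.2236 SD. The false-positive rate is the rejection probability of a two-sided t test on 78 degrees of freedom with noncentrality bias / 0.2236.

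| Gap | Correlation | Bias | Share of 0.63 | Noncentrality | False-positive rate |
|---|---|---|---|---|---|
| 0 | any | 0 | 0% | 0 | 5.0% |
| 0.3 | 0.3 | 0.09 | 14% | 0.40 | 6.8% |
| 0.5 | 0.3 | 0.15 | 24% | 0.67 | 10.2% |
| 0.8 | 0.4 | 0.32 | 51% | 1.43 | 29.3% |

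On the plan's scales, 0.09 to 0.32 SD is 0.58 to 2.08 for peak fetal heart rate (× 6.49; design difference 4.12) and 0.06 to 0.22 for an NNNS subscale (× 0.70; design difference 0.44).

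**Step 3. Does a route match remove it?** A simulation with 3,000 runs per setting matched exactly on binary route and put route in the model. Assumptions: severity gap before matching 0.3 to 0.8 SD; severity-outcome correlation 0.3 or 0.5; severity-route correlation 0.4 or 0.7 on the latent scale; an ASI-type score with reliability 0.8, not itself affected by treatment.
- Route only: 0.20 to 0.73 SD of the gap remained, bias was 0.07 to 0.36 SD, and the false-positive rate was 5% to 37%.
- ASI-type score added: bias was 0.02 to 0.08 SD and the false-positive rate about 5% to 6%.
- No true gap: bias was below 0.01 SD either way.

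**Step 4. Which estimates are exposed.** In 1c the estimate is the peak-by-BN term, a between-group difference in within-woman peak-minus-trough differences. If severity adds the same amount at peak and at trough, it cancels within each woman. Only a severity-by-peak interaction biases the term, and a main effect for the ASI leaves it essentially unchanged. The same reasoning applies to the BN-by-time terms in 2a, 4b and 4c, which need a severity-by-time interaction. The direct exposure is in the level contrasts.

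**The case against.** **Imbalance is not demonstrated.** A reader might infer that the drug groups will be unbalanced on severity, or that severity is a main reason why women receive one drug rather than another. The documents support neither. They contain no baseline severity data, and they say only that women accept or request buprenorphine. This stands, and it limits the point to a lack of protection.

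**Not every contrast is affected.** A reader might extend the bias to 1c and the trajectory terms. Step 4 shows why an ASI main effect would neither reveal nor remove a problem there. This stands.

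**The ASI may not be a pre-treatment measure.** Methadone women are drawn from those already maintained, and stable B+N women skip induction. Past-30-day items can therefore reflect the treatment under comparison, and adjusting for them could remove part of a drug effect. This stands and shapes the fix.

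**The plan may already cover part of this.** The match list may be incomplete, the ASI could supply the non-opioid substance-use covariate, that covariate may absorb part of a severity gap, and Section 7b says its analyses are not exhaustive. These points stand in part. But severity is defined by route, a non-opioid covariate does not measure opioid severity, and the general disclaimer does not override a named adjustment set. Leaving the covariate open would also let it be chosen after the data are seen.

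**The historical group is not wholly dissimilar.** Section 3 says that earlier studies recruited from the same clinic under essentially the same criteria. That helps, but it is not a severity match. Section 4a shows ASI use in the prior study only for alcohol screening, so usable drug or psychological scores may not exist.

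**Conclusion.** The point holds in a limited form. Against confounding by opioid-use severity, the plan describes only a binary route match, and only for the methadone comparison. It describes no match for the historical comparison and no severity or psychiatric score in any group model. A suitable measure is already collected on every enrolled woman.

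The range of 0.09 to 0.32 SD bias and about 7% to 29% false positives rests entirely on an assumed residual gap of 0.3 to 0.8 SD and a correlation of 0.3 to 0.4. It also treats the planned covariates as absorbing none of the gap. The direction of any bias is unknown. For the hypotheses that predict similarity, a false-positive rate does not describe the relevant error, which is a masked difference. The change should be made because it is cheap and closes an avoidable gap, not because a wrong result has been shown.

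**What to change.** Amend Section 7b before any group comparison is run:

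1. **Level contrasts (2a, 2b, 3b, 3c, 4b, 4c).** Add route of administration and the enrolment ASI drug-use and psychological measures as pre-specified covariates; keep the route match. Use lifetime or pre-treatment ASI items in the main model, and past-30-day items only in a sensitivity analysis.
2. **1c and the trajectory terms.** Add ASI-by-peak or ASI-by-time interactions as sensitivity analyses only.
3. **Balance.** Report the ASI measures by group among completers.
4. **Historical group.** If ASI scores are available, show results with and without the adjustment. If they are not, state that this comparison is unadjusted for severity.
5. **Match list.** Restore the missing text in Section 4a so that the full set of matching factors can be read.

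The cost is wording plus a few degrees of freedom per model; enrolled women need no new visits or instruments. The downsides are possible missing ASI data in the historical group and some over-adjustment wherever on-treatment items are used.
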